### **11.3.3. Study Discontinuation**

The sponsor reserves the right to terminate the study at any time. Should this be necessary, both parties will arrange discontinuation procedures and notify the appropriate regulatory authority(ies), IRBs, and IECs. In terminating the study, Axovant Sciences Ltd. and the investigator will assure that adequate consideration is given to the protection of the subjects' interests. The investigator may discontinue participation in the study at any time. However, the obligations to provide study results for completed subjects and reports to ethics committees shall continue as required by this protocol and applicable laws and regulations.

1 INTRODUCTION

The purpose of this Statistical Analysis Plan (SAP) is to describe the detailed methodology for summary and statistical analyses to be performed following the completion of Study RVT-101-2003, a Phase 2, double-blind, randomized, placebo-controlled crossover study evaluating the effect of RVT-101 on gait and balance in subjects with Alzheimer’s Disease, Dementia with Lewy Bodies, or Parkinson’s Disease Dementia.

Study measurements and assessments, planned statistical methods, and derived variables are summarized in this plan. Planned tables, figures, and listings are specified in a separate spreadsheet. All decisions regarding final analyses, as defined in this SAP document, have been made prior to locking the database.

[figure not shown]
1.1 Study Design

This is a multi-center, double-blind, randomized, placebo-controlled, crossover study in dementia subjects with gait impairment. The primary objective of the study will be to evaluate the effect of intepirdine on gait speed. The secondary objective is to assess the safety and tolerability of intepirdine. Exploratory objectives of the study include the evaluation of the effects of RVT-101 on other quantitative and qualitative measures of gait and balance.

Following an initial screening period, eligible subjects will enter a two-week single-blind placebo run-in period (Period I). At the end of this period, all subjects who continue to meet the eligibility criteria will enter the first two-week double-blind treatment period (Period II). Following the completion of Period II, subjects will undergo a washout period (Period III) of two weeks during which subjects will receive placebo. After the two-week washout, subjects will enter the second two-week double-blind treatment period (Period IV). A safety follow-up telephone call will be conducted approximately 2 weeks after completion of Period IV.

Figure 1 provides a study scheme demonstrating the key design elements and scheduled study visits.

Figure 1. Study Design

1.2 Study Objectives

1.2.1 Primary Objective

The primary objective of this study is to assess the effect of intepirdine versus placebo on gait speed, a quantitative measure of functional mobility, on an electronic walkway system after 2 weeks of treatment.

1.2.2 Secondary Objective

Secondary objective is to assess the safety and tolerability of intepirdine.

1.2.3 Exploratory Objectives

Exploratory objectives of this study are:

- To assess the effect of intepirdine versus placebo on gait variability on an electronic walkway system after 2 weeks of treatment
- To assess the effect of intepirdine versus placebo on gait and balance, as measured by the Mini Balance Evaluation Systems Test (mini-BESTest) battery total score and individual subscores, after 2 weeks of treatment
- To assess the effect of intepirdine versus placebo on gait and balance, as measured by individual item scores calculated by Opal APDM sensors during performance of the mini-BESTest battery, after 2 weeks of treatment at sites where the technology and capability is available
- To assess the effect of intepirdine versus placebo on freezing of gait (FOG), as measured by clinical and quantitative scores, after 2 weeks of treatment
- To assess the effect of intepirdine versus placebo on movement and balance, as measured by the Movement Disorder Society - Unified Parkinson's Disease Rating Scale (MDS-UPDRS) Parts II and III, Postural Instability and Gait Difficulty (PIGD), and MDS-UPDRS 7-Item subscore, after 2 weeks of treatment
- To assess the effect of intepirdine versus placebo on smell, a proxy for cholinergic function, as measured by the University of Pennsylvania Smell Identification Test (UPSIT), after 2 weeks of treatment

1.3 Sample Size Considerations

The primary comparison of interest is to compare the efficacy of intepirdine to placebo after a two-week treatment period in subjects with Alzheimer's Disease (AD) or Lewy body dementia (LBD). LBD is an umbrella term that includes both Dementia with Lewy Bodies (DLB) and Parkinson's Disease Dementia (PDD). A sample size of approximately 30-40 subjects (comprised of approximately 15-20 AD subjects and approximately 15-20 LBD subjects) will be included in this study. No formal power calculations were performed.

1.4 Randomization and Stratification

Each subject will be randomized 1:1 to one of the following sequences:

- Sequence 1: AB = Intepirdine in Period II and Placebo in Period IV
- Sequence 2: BA = Placebo in Period II and Intepirdine in Period IV

Randomization will be stratified according to Mini Mental State Examination (MMSE) score in the groups of 14-19 points and 20-26 points. Randomization will also be stratified according to whether subjects have AD or LBD.

1.5 Nomenclature

For purposes of this SAP, as well as in the analysis tables, figures, and listings, the study drug is referred to as “intepirdine”. The study drug is also referred to (eg, in the protocol) as RVT-101.

2 STUDY ENDPOINTS

2.1 Co-Primary Endpoints

The co-primary endpoints in this study are:

- Change from baseline in gait speed measured on an electronic walkway system under single task trial condition at the end of each two-week treatment period
- Change from baseline in gait speed measured on an electronic walkway system under dual task trial condition at the end of each two-week treatment period

2.2 Secondary Endpoints

Secondary endpoints include occurrence of adverse events (AEs) and changes in physical examinations, vital signs measurements, electrocardiograms (ECGs), routine laboratory assessments, and Columbia Suicide Severity Rating Scale (C-SSRS).

Secondary endpoints are discussed in the Safety Analysis section of this SAP.

2.3 Exploratory Endpoints

The exploratory endpoints in this study are:

- Change from baseline in step time variability and step length variability measured on an electronic walkway system at the end of each treatment period
- Change from baseline in the mini-BESTest total score and individual subscores at the end of each treatment period
- Change from baseline in individual item scores calculated by Opal APDM sensors during performance of the mini-BESTest battery at the end of each treatment period

- Change from baseline in the FOG score and freezing ratio, incorporating input from Opal APDM sensors during turning conditions, at the end of each treatment period
- Change from baseline in MDS-UPDRS Parts II and III subscores, PIGD, and MDS-UPDRS 7-Item subscore at the end of each treatment period
- Change from baseline in UPSIT score at the end of each treatment period

2.4 Description of Efficacy Endpoints

2.4.1 Gait Speed

Electronic walkway systems, such as the GAITRite and Zeno Walkway system, are computerized assessment tools that utilize an electronic mat consisting of pressure-sensitive pads that can calculate spatiotemporal gait parameters which include gait speed (Buesing et al., 2015) as the primary efficacy endpoint.

Subjects will undergo the gait assessments under single and dual task conditions, each with 3 trials, at all study visits. All assessments will be done on the Zero Walkway system. The PKMAS software will be utilized to capture and process gait data in the study. The average of the 3 measurements will be used in the statistical analysis.

Each co-primary outcome measures (ie, gait speed assessed under single and dual task conditions) in this study will be tested at two-sided 5% level of significance.

2.4.2 Step Time and Length Variability

Step time variability and step length variability, similarly to gait speed are calculated during the electronic walkway system assessment. The calculated endpoints will be directly obtained from the electronic walkway system and will be utilized in statistical analysis separately by single and dual task conditions.

- Change in step time variability as measured on an electronic walkway system from the start to the end of each treatment period with intepirdine
- Change in step length variability as measured on an electronic walkway system from the start to the end of each treatment period with intepirdine

2.4.3 Mini Balance Evaluation Systems Test (Mini-BESTest)

The Mini-BESTest is a short, validated 14-item assessment of dynamic balance, specifically anticipatory postural transitions, postural responses, and dynamic gait (King et al., 2012). Each item is scored from 0-2 with a score of 2 being normal. The total score is out of 28. The analysis will be performed on the total score and individual subscores. The subscales are:

- Anticipatory: the total subscore is out of 6
- Reactive postural control: the total subscore is out of 6
- Sensory orientation: the total subscore is out of 6

- Dynamic gait: the total subscore is out of 10

2.4.4 Mini Balance Evaluation Systems Test (Mini-BESTest) Analyzed by OPAL Sensors

The Mini-BESTest assessment will be performed with subjects wearing the Opal APDM sensors if available at the site, which will collect quantitative measures of dynamic gait and balance as captured by the Mobility Lab Software. The following measurements calculated by Opal APDM sensors during performance of the mini-BESTest battery will be utilized in statistical analysis.

- MiniBest Item 1: Sit to stand
- MiniBest Item 3: Stand on one leg
- MiniBest Item 7: Stance (feet together)
- MiniBest Item 8: Stance (feet apart on foam surface)
- MiniBest Item 9: Stance (feet apart on firm surface)

2.4.5 Freezing of Gait (FOG) Assessment

FOG is a symptom where subjects experience a paroxysmal inability to either continue or initiate gait (Shine et al., 2011). FOG is an independent risk factor for future falls in PD (Latt et al., 2009).

- In this study, freezing of gait will be assessed while subjects perform a procedure involving multiple turns. Subjects will wear Opal APDM sensors while performing this procedure, which will provide quantitative data related to freezing of gait. The calculated FOG ratio is evaluable only if duration of turn is at least 50 seconds ([name], personal communication, November 21, 2017).
- Additionally, the freezing of gait assessment will be done by a rater. This freezing severity will be on a 0 to 4 scale: 0, Absent (no freezing episodes); 1, Mild (hesitation or episodic slowing); 2, Moderate (at least arrest); 3, Severe (multiple arrests); 4, Unable (required assistance).

2.4.6 Movement Disorder Society-Unified Parkinson's Disease Rating Scale (MDS-UPDRS) Parts II and III

The MDS-UPDRS is considered the 'gold standard' clinical scale for PD (Song et al., 2009). The MDS-UPDRS is a revision of the original UPDRS (Goetz et al., 2008) made by the Movement Disorder Society. Part II of the MDS-UPDRS is a questionnaire that focuses on motor aspects of experiences of daily living (13 items, score range: 0 to 52) and Part III (18 items, 33 ratings, score range: 0 to 132) is a motor examination. Each item on the MDS-UPDRS is rated on a 0 to 4 scale, where 4 represents the worst disability and 0 represents no disability. Part II and Part III totals will be analyzed separately and then combined.

The PIGD 4-item subscale of MDS-UPDRS Part III (ie, posture, gait, postural stability, arising from chair) focuses on items related to postural instability and gait difficulty which are highly correlated with fall risk (Rudzinska et al., 2007) and deficits of executive function (Xu et al., 2014). The scale measurement range is 0 to 16.

The MDS-UPDRS 7-item subscale of MDS-UPDRS Part III (ie, facial expression, rigidity, global spontaneity of movement, postural tremor of hands [right, left], kinetic tremor of hands [right, left], rest tremor amplitude, constancy of rest tremor) was found to have high specificity and sensitivity for cognitively impaired patients with extrapyramidal features (Ballard et al., 1997) and can be computed as the sum of numeric responses to MDS-UPDRS Part III items 2, 3 (5 ratings), 14, 15 (2 ratings), 16 (2 ratings), 17 (5 ratings) and 18, with subscale scores ranging from 0 to 68 (inclusive).

2.4.7 University of Pennsylvania Smell Identification Test (UPSIT)

Approximately 90% of subjects with early stage PD have olfactory dysfunction, and olfactory dysfunction correlates with loss of cholinergic neurons in structures such as the nucleus basalis of Meynert (nBM) (Doty, 2012; Mancini and Horak, 2010). The UPSIT is a 40-item ‘scratch-and-sniff’ test that takes about 15 minutes to administer and is a reliable measure of olfactory function. The result of the test is the number of items correctly identified.

3 ANALYSIS POPULATIONS

It is intended that a complete accounting of subjects for the analysis populations will be provided, from the Screened Population through the Completers Population.

3.1.1 Screened Population

All subjects who have signed an informed consent and completed the screening phase will be included in the Screened Population.

3.1.2 Run-In Population

All subjects entering the Placebo Run-in will be included in the Run-In population. This population will be used to provide an accounting of the disposition of subjects during this phase of the study.

3.1.3 Randomized Population

The Randomized Population will include all subjects who are randomized.

3.1.4 Safety Population

The Safety Population will consist of all subjects who were randomized and took at least one dose of double-blind investigational product.

3.1.5 ITT Population

The Intent-to-Treat (ITT) Population will consist of all subjects randomized to treatment who have taken at least one dose of double-blind investigational product and have an evaluable baseline assessment and a valid post baseline primary efficacy assessment during double-blind treatment period. This will be the primary population used for the efficacy analysis.

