### **10.3. Data Analysis Considerations**

#### **10.3.1. Analysis Populations**

The primary population for safety analyses will be the Safety Population, which will consist of all subjects who were randomized and took at least one dose of investigational product.

The efficacy analysis population will consist of all randomized subjects who have taken at least one dose of investigational product and who have at least one post-baseline efficacy assessment. This will be the primary population used for the efficacy analysis.

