4.3.2 Missing Walkway Data

No values will be imputed for missing data. If one of the triplicate measurements for a Gait parameter are missed, the average of the remaining two measurements can be used in the analyses. If two of or all the triplicate measurements are missing at a timepoint for a Gait parameter, no values will be imputed or calculated for this timepoint.

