6.4 Analysis of the Exploratory Efficacy Endpoints

Continuous and ordinal variables will be analyzed in a fashion similar to that of the primary endpoints, using the mixed model for crossover design on the ITT dataset.

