9 CHANGES FROM THE PROTOCOL TO THIS SAP

There are no meaningful changes from the protocol to this SAP. Additional details and specifications have been included in this SAP to allow for better understanding of the intended procedures.

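### SAP 3.1.5 makes a valid walkway assessment the entry condition for non-walkway exploratory endpoints too, an undeclared narrowing of the protocol's efficacy population (minor)

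*SAP*

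**What the plan says.** Protocol 10.3.1 defines the efficacy population as randomized subjects who took at least one dose and "who have at least one post-baseline efficacy assessment". It does not restrict the kind of assessment and sets no baseline condition.

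SAP 3.1.5 defines the ITT population more tightly. Besides randomization and a double-blind dose, subjects must "have an evaluable baseline assessment and a valid post baseline primary efficacy assessment during double-blind treatment period". The section adds: "This will be the primary population used for the efficacy analysis".

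SAP 2.1 names two co-primary endpoints, both from the walkway: "Change from baseline in gait speed measured on an electronic walkway system under single task trial condition at the end of each two-week treatment period" and "Change from baseline in gait speed measured on an electronic walkway system under dual task trial condition at the end of each two-week treatment period".

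SAP 6.4 has the exploratory endpoints analysed like the primary ones, "using the mixed model for crossover design on the ITT dataset". SAP 6.4.1 lists them: step time and step length variability, mini-BESTest, Opal sensor measures, FOG, MDS-UPDRS and its subscores, and UPSIT.

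If two or three of the three walkway trials are missing at a visit, SAP 4.3.2 says "no values will be imputed or calculated for this timepoint".

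SAP 9 states: "There are no meaningful changes from the protocol to this SAP". SAP 4.2 gives the SAP precedence where the two documents differ.

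**The concern.** A condition written for gait speed decides who is analysed on endpoints that are not gait speed. UPSIT is a smell test and MDS-UPDRS Part II is a questionnaire; neither uses the walkway. The mixed model runs on observed data, so a subject with no value for an endpoint already drops out of that endpoint's model. For a non-walkway endpoint, the walkway condition can therefore only remove usable data. It gives nothing in return.

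At stake are some precision on the non-walkway exploratory endpoints in a trial of 30 to 40 subjects, and a change to the primary efficacy population that a reader of SAP 9 would not know had been made.

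**Working it through.** The plan has no figure of its own to reproduce: SAP 1.3 says no power calculation was done, and neither document gives a rate of missing walkway data. The check is a comparison of definitions, followed by an illustration of size.

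**Definitions side by side**

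| | Protocol 10.3.1 | SAP 3.1.5 |
|---|---|---|
| Dose | at least one of investigational product | at least one double-blind |
| Baseline | no condition | evaluable; endpoint not named |
| Post-baseline | any efficacy assessment | valid primary assessment (walkway gait speed, by SAP 2.1) |

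**Can another planned set bring the subject back?** No. SAP 6.1 tabulates efficacy for the ITT, per-protocol and completers sets. SAP 3.1.6 and 3.1.7 define the latter two as members of the ITT population.

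**Who is actually lost?**

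1. SAP 3.1.5 asks for one valid post-baseline primary assessment and does not ask for one per period. A subject with a usable walk at Visit 4 or Visit 6 stays in. Loss by this route needs an unusable walk at both visits, together with usable data on another scale.
2. The baseline route is less certain. SAP 4.1.2 sets a baseline for each period, and SAP 4.3.4 invalidates a late baseline for the assessment being analysed. It removes a subject only if the evaluable baseline in SAP 3.1.5 means a walkway one and the subject has none.
3. Subjects who leave before Visit 4 do not count towards the difference. The early termination column of protocol Table 2 schedules no efficacy test, so they would normally fail both definitions.
4. Use of a walking aid does not by itself exclude. Table 2 lets some such subjects skip the Primary Gait Screen, but protocol 8.2 has all subjects do the single and dual task walks.

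**Size.** Let N be the number who could contribute to an endpoint and k the number lost through the walkway condition. If each lost subject would have given complete data in both periods, and all subjects carry equal information, the standard error (SE) is multiplied by sqrt(N/(N−k)).

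| k (assumed) | N=30 | SE rise | N=40 | SE rise |
|---|---|---|---|---|
| 1 | sqrt(30/29) = 1.017 | 1.7% | sqrt(40/39) = 1.013 | 1.3% |
| 2 | sqrt(30/28) = 1.035 | 3.5% | sqrt(40/38) = 1.026 | 2.6% |
| 3 | sqrt(30/27) = 1.054 | 5.4% | sqrt(40/37) = 1.040 | 4.0% |
| 4 | sqrt(30/26) = 1.074 | 7.4% | sqrt(40/36) = 1.054 | 5.4% |

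This applies to mini-BESTest, Opal, FOG, MDS-UPDRS and UPSIT. It does not apply to step time and step length variability: SAP 2.4.2 takes them from the same walkway assessment, so a subject with no usable walk contributes nothing to them under either definition. The same holds for gait speed.

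**The case against.** The strongest reply is that the affected group is nearly empty. Inclusion criterion 10 requires ability to comply with gait testing, and randomized subjects should already have walked at Visits 1 to 3. Protocol 8.1 puts the walkway first among the motor tests and lets testing be rescheduled within the visit window. A subject must then fail at both Visit 4 and Visit 6 while giving other efficacy data. This stands, and it is why the point is minor. It does not remove the mismatch between the documents or give the filter a purpose.

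It can also be said that protocol 10.3.1 could not be applied literally, because a change-from-baseline model needs a baseline for its endpoint. That is right. The remedy is a third definition and should be declared as one.

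Several stronger readings are tempting, and the documents do not support them:

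- *One failed walkway session removes the subject.* SAP 4.3.2 blanks a timepoint; it does not remove a subject.
- *A late walkway baseline removes the subject.* Baselines are set by period, and SAP 4.1.5 assumes that same-day Visit 3 and Visit 5 assessments preceded the dose.
- *The excluded subjects are the most gait-impaired, so the results are biased.* This is possible, but neither document gives reasons for missing walks, and equipment or software failure would have the same effect. The treatment contrast is largely within-subject, and no bias in it has been shown.
- *Every exploratory contrast loses precision.* The step variability endpoints do not.
- *The data are thrown away.* SAP 4.2 keeps case report form data in listings, SAP 6.1 says only that tabulations will generally use the named sets, and SAP 6.4.3 allows further sensitivity analyses.

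**Conclusion.** The point holds in a limited form. SAP 3.1.5 narrows the protocol's efficacy population, SAP 6.4 carries the narrowed set to endpoints that do not depend on the walkway, no other planned set reverses it, and SAP 9 does not report it.

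The consequence is a possible loss of precision on the non-walkway exploratory endpoints: about 1.7% to 7.4% in standard error at N=30, or 1.3% to 5.4% at N=40. Those figures rest on an assumed 1 to 4 affected subjects, each with otherwise complete data. The true number cannot be found from the documents and is probably small.

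The co-primary endpoints and step variability are unaffected, on the reading that a valid gait speed in either task condition satisfies SAP 3.1.5. The SAP does not say so. If both conditions were required, a subject who walks but cannot do the dual task would also fall outside the set, and that subject's single-task result would go too.

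Severity: minor.

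**What to change.** In SAP 6.4, replace the ITT dataset for the non-walkway exploratory endpoints with an endpoint-specific set: all randomized subjects who took at least one double-blind dose and have, in at least one double-blind period, a valid period baseline and a post-baseline value for the endpoint being analysed. Keep the walkway-based ITT for the co-primary endpoints.

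In SAP 9, list two departures from protocol 10.3.1: the ITT definition in SAP 3.1.5 and this endpoint-specific set. While SAP 3.1.5 is open, state which assessment needs the evaluable baseline and whether one or both task conditions must be valid.

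The cost is a few sentences and one population flag per endpoint. Subject numbers may differ slightly between endpoint tables, so each table should show its own N. The co-primary analysis does not change.
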